MH	macular hole
MI	multiple imputation
MP	microperimetry
MMRM	mixed model for repeat measurements
MNAR	Missing Not at Random
OD	oculus dextrus (right eye)
OS	oculus sinister (left eye)
OU	oculus uterque (both eyes)

CONFIDENTIAL

Statistical An	alysis Plan	: 273CH301	/NSR-REP-01
	-		11FEB2021

P05	5 th percentile
P95	95 th percentile
PBMC	peripheral blood mononuclear cells
PP	per protocol
PT	preferred term
Q1	first quartile
Q3	third quartile
REP1	Rab Escort Protein 1
RPE	retinal pigment epithelium
SAE	serious adverse event
SAP	statistical analysis plan
SD	standard deviation
SD-OCT	spectral domain optical coherence tomography
SFU	spot forming units
SOC	system organ class
SRF	subretinal fluid
TEAE	treatment-emergent adverse event
TOF	targeted ocular findings
VFQ	visual function questionnaire
vg	viral genomes
VMT	vitreomacular traction
WHO	World Health Organisation
WHODD	Who-Drug Dictionary

1 INTRODUCTION

This document presents the statistical analysis plan (SAP) for Biogen / NightstaRx Ltd, Protocol No. 273CH301 / NSR-REP-01: A Randomized, Open Label, Outcomes-Assessor Masked, Prospective, Parallel Controlled Group, Phase 3 Clinical Trial of Retinal Gene Therapy for Choroideremia Using an Adeno-Associated Viral Vector (AAV2) Encoding Rab Escort Protein 1 (REP1) (STAR Study).

AAV2-REP1 is denoted hereafter by the USAN timrepigene emparvovec (BIIB111).

The purpose of this SAP is to ensure that the efficacy and safety analyses prespecified by statistical methodologies provide appropriate definitions for summary tables, figures, and data listings.

2 STUDY OBJECTIVES

The objective of the study is to evaluate the efficacy and safety of a single sub-retinal injection of timrepigene emparyovec in subjects with choroideremia (CHM).

3 OVERVIEW OF STUDY DESIGN

3.1 Discussion of Study Design

This is an outcomes-assessor masked, prospective, randomized, parallel- controlled group, multi-center, global, interventional study. The study consists of 8 visits with a 12-month evaluation period (Figure 1). During the Screening/Baseline Period, each subject will be assessed for eligibility. If a subject has only 1 eligible eye, that eye will be designated as the "study eye" and the subject's other (non-eligible) eye will be designated as the "fellow eye." If a subject has 2 eligible eyes, the selection of the "study eye" will be made on clinical grounds and will generally be the worse eye affected.

For eligible subjects, a study eye will be assigned, and the subjects will be randomized in a 2:1:2 ratio to receive either timrepigene emparvovec high dose $(1.0 \times 10^{11} \text{ viral genomes [vg]})$, timrepigene emparvovec low dose $(1.0 \times 10^{10} \text{ vg})$ or to enter the untreated Control group. Once a subject has been randomized, a change in "study eye" designation is not permitted.

At the time of randomization, a projected surgical date should be defined for each subject. For each subject randomized to the control group, this projected surgical date (+/-1 day) should remain the Day 0 (Visit 2) date. For each subject randomized to a treated group, Day 0 (Visit 2) will be the actual date of surgery. The Screening / Baseline period must occur within 8 weeks prior to dosing (Week 2, Day 0).

Study data will be collected for both eyes of each subject.

Since timrepigene emparvovec treatment requires an invasive surgical procedure under general anesthesia, the sponsor, investigator and the subject will be unmasked to the study procedure (i.e. vitrectomy and sub-retinal injection), however within the treated groups, the sponsor, investigator and subject will be masked to the assigned dose $(1.0 \times 10^{11} \text{ vg or } 1.0 \times 10^{10} \text{ vg})$. To further minimize the potential bias of the treated and untreated eye evaluations, all subjective ophthalmic assessments from the Screening/Baseline period (Visit 1) and from Month 1 (Visit 5) onwards, will be conducted by a masked assessor.

Figure 1Overall Study Schematic

3.2 Study Treatment

The AAV2 vector contains recombinant human cDNA encoding REP1 (timrepigene emparvovec). The vector genome (AAV2-CBA-hREP1-WPRE-BGH) consists of a strong constitutive expression cassette, a hybrid chicken beta actin promoter, the human cDNA encoding Rab escort protein-1 (REP1), a modified woodchuck hepatitis post-transcriptional regulatory element sequence, and a bovine growth hormone polyadenylation sequence flanked by AAV2 inverted terminal repeats. The cDNA fragment was originally isolated from a human retinal cDNA library from unaffected individuals.

The timrepigene emparvovec drug product is formulated in a sterile, 20 mM Tris-buffered solution, pH 8.0, and contains 1 mM MgCl₂, 200 mM NaCl and 0.001% PF68. The drug product is a clear to slightly opalescent, colorless, sterile-filtered suspension with a target concentration of 1.0×10^{12} vg/mL.

Timrepigene emparvovec will be administered in the study eye (i.e., the treated eye) as a subretinal injection following vitrectomy.

3.3 Study Schedule

At each study visit, an attempt should be made to perform all procedures/collect the data in both eyes, unless otherwise specified (Appendix 2: Schedule of Study Procedures).

A subject is considered to have completed the study if he completes the Month 12 assessments. The end of the study is the date the last subject completes his Month 12 assessments (or early termination [ET] assessments in the event of premature discontinuation) or the date of last data collection if the last subject is lost to follow-up.

3.4 Randomization

During the Screening/Baseline period, all subjects will be assigned a screening identifier, which will include the center number and subject number. If the subject fulfils all eligibility criteria during the Screening/Baseline period, a study eye will be assigned (prior to randomization) and the subject will be randomized in a 2:1:2 ratio to receive either timrepigene emparvovec high dose $(1.0 \times 10^{11} \text{ vg})$, timrepigene emparvovec low dose $(1.0 \times 10^{10} \text{ vg})$ or to enter the untreated Control group.

Randomization will be generated using a validated system that automates the random assignment of treatment groups and stratified by surgical group*. Once a subject is deemed

Biogen /	NightstaRx,	Ltc
BIIB111		

eligible, the investigative site (or authorized designee) will access the system, and the subject will be randomized using a standard blocked randomization.

Once a subject has been randomized, a change in "study eye" designation is not permitted.

At the time of randomization, a projected surgical date should be defined for each subject. For each subject randomized to the control group, this projected surgical date (+/-1 day) should remain the Day 0 (Visit 2) date. For each subject randomized to a treated group, Day 0 will be the actual date of surgery.

All subjects' data (including screen failures) will be entered into the electronic case report form (eCRF).

* A surgical group will consist of a single 'Surgical Site' and 'Non-surgical Sites'. The Surgical Site will conduct baseline and follow-up visits for local subjects, as well as surgeries and immediate post-operative visits for all subjects treated in the surgical group. The 'Non-surgical Sites' will only perform the baseline/screening visit and the follow-up visits from Day 7 (Visit 4) onwards for their respective local subjects.

3.5 Study Masking

Randomization of subjects aims to minimize potential selection bias.

Given a double-masked design is not feasible (i.e. treatment involves invasive surgical procedure under general anesthesia), the sponsor, investigator and the subject will be unmasked to whether a subject has been assigned to the timrepigene emparvovec treatment groups, or the untreated Control group. However, within the treated groups, the sponsor, investigator and subject will be masked to the assigned dose $(1.0 \times 10^{11} \text{ vg or } 1.0 \times 10^{10} \text{ vg})$. To further minimize potential performance/detection bias, all subjective ophthalmic assessments at the Screening/Baseline Period (Visit 1) and from Month 1 (Visit 5) onwards, will be conducted by a masked (outcomes) assessor.

Additional measures to minimize potential performance/detection bias include standardized methodologies across participating sites (same equipment, assessor training/certification, surgical training), and an identical visit/assessment schedule for treated/untreated patients.

3.6 Sample Size

Approximately 160 subjects will be enrolled in the study (64, high dose group; 32, low dose group; 64, control group).

The sample size calculation is based on a Fischer's exact test. CHM is a degenerative disease, it is therefore assumed that a \geq 15 letter BCVA gain would not be observed in subjects without CHM treatment. Assuming that 16.7% of the treated subjects will gain \geq 15 letters BCVA at Month 12, 56 subjects in the high dose group and the control group provide at least 90% power at a 0.05 level of significance with a 2-sided test. To be conservative, 64 patients in the high dose group and 64 patients in the control group are needed to ensure 85% power in case 1 patient in the untreated control group has \geq 15 letter BCVA gain by chance, which corresponds to a total of 160 patients completing the study.

4 STUDY ENDPOINTS

4.1 Primary Efficacy Endpoint

The primary efficacy endpoint is the proportion of subjects with a \geq 15-letter improvement from Baseline in best corrected visual acuity (BCVA) at Month 12 as measured by the Early Treatment of Diabetic Retinopathy Study (ETDRS) chart.

4.2 Key Secondary Efficacy Endpoints

There are 3 key secondary efficacy endpoints:

- 1. Change from Baseline in BCVA at Month 12 measured by the ETDRS chart
- 2. Proportion of subjects with a ≥10-letter improvement from Baseline in BCVA at Month 12 measured by the ETDRS chart
- 3. Proportion of subjects with no decrease from Baseline in BCVA or a decrease from Baseline in BCVA of <5 ETDRS letters at Month 12 measured by the EDRS chart

4.3 Other Secondary Efficacy Endpoints

Secondary efficacy endpoints include:

- Change from Baseline in BCVA at Months 4 and 8
- Change from Baseline in total area of preserved autofluorescence (AF) at Month 12
- Change from Baseline in the area of preserved ellipsoid zone (spectral domain optical coherence tomography [SD-OCT]) at Month 12
- Change from Baseline in microperimetry at Month 12
- Change from Baseline in contrast sensitivity score at Month 12
- Change from Baseline in colour vision at Month 12
- Change from Baseline in reading speed test at Month 12
- Change from Baseline in the 25-item Visual Function Questionnaire (VFQ-25) at Month 12

4.4 Exploratory Efficacy Endpoints

4.5 Safety Endpoints

The safety endpoints are:

- Overall adverse events (AEs), serious AEs (SAEs), and AEs (or SAEs) leading to discontinuations
- Clinical laboratory evaluations
- Vital signs including diastolic blood pressure, systolic blood pressure, and pulse

5 GENERAL ASPECTS FOR STATISTICAL ANALYSIS

5.1 General Methods

All analyses and summaries will be produced using SAS® version 9.4 (or higher).

For descriptive summary statistics, the efficacy and safety data will be summarized and displayed by treatment groups (Control, Low Dose, High Dose) and visits (Baseline, Month 1, 4, 8, 12, and End of Study).

Summary statistics will be presented for continuous variables, by way of number of subjects, mean, standard deviation (SD), median, first and third quartiles (Q1 and Q3, respectively), 5th and 95th percentiles (P05 and P95, respectively), minimum and maximum. Where specified, the 95% Confidence Interval (CI) of the mean will be calculated. Summary statistics will be presented where appropriate by treatment and nominal visit with an additional entry for the end of study.

For categorical variables (including binary variables), counts and percentages will be presented. Where specified, the 95% 2-sided CI for proportions will be calculated.

The listings, except the listing for screen failures, will include all randomized subjects in the database. In general, the subject listings will be sorted by treatment group, subject number, eye (starting with the study eye) and assessment date (and time, if applicable).

Data for unscheduled assessments will be included when calculating baseline values, selecting worst result for shift analyses, and for summary of normal/abnormal values. The safety summary of observed and change from baseline data will be performed by nominal (i.e., scheduled) visits. Unscheduled visits will be included in the analysis of End of Study, i.e., the last available non-missing treatment endpoint.

5.2 Baseline Value

Baseline is defined as a value recorded at Visit 1 prior to treatment. Where this value is missing or unavailable, then an available Visit 2 (prior to treatment) result will be used.

- If there is more than one BCVA assessment, the median value will be used as baseline.
- If there is more than one microperimetry assessment, the most recent value will be used as baseline.

5.3 Study Day

Study day is defined as the number of days from the date of treatment (or phone contact for the untreated control group) to the event/visit date. It is calculated as follows:

If the event date falls on the date of treatment, or after the date of treatment then:

Study Day = Event or Visit Date – Treatment Date + 1

If the event date falls before the date of treatment then:

Study Day = Event or Visit Date – Treatment Date

CONFIDENTIAL

5.4 Missing Data

If a subject discontinues the study prematurely, missing data handling will be specified in Section 5.5 and Section 10 EFFICACY ANALYSIS.

The AE and concomitant medication start/end dates will be imputed based on the rules described in Appendix 3.

5.5 Statistical Analyses Handling of Data Impacted by COVID-19

Currently there is an outbreak of respiratory disease caused by a novel coronavirus (COVID-19). In accordance with the newly released FDA guidance 'Statistical Considerations for Clinical Trials During the COVID-19 Public Health Emergency (June 2020)', alternative data ascertainment methods at an operational level are being explored such as using local nonstudy sites while international and interstate travel is limited due to COVID-19. In case an assessment is performed using the local non-study sites, subjects will be encouraged to attend their protocol-defined study sites for an ad-hoc visit (i.e., unscheduled visits) during which the per-protocol Month 12 assessments will be performed. Also, in line with the guidance, extension of the protocol-defined window aiming to include out-of-window visits is considered for performing the endpoint ascertainment. Data collected via these two approaches (assessment at local non-study sites, if applicable, as well as out of window visits) are further referred to as 'alternative data ascertainment'.

In terms of the statistical analysis, the impact of the COVID-19 pandemic on the STAR study will be evaluated by summarizing the number and percentage of subjects, by treatment and overall:

- Who died during the study due to COVID-19;
- Who withdrew from the study due to COVID-19;
- Who had alternative data ascertainment at Month 12 due to COVID-19;
 - o via the assessment at local non-study sites, if applicable
 - via the extension of out-of-window visits
- Who still missed their Month 12 visit due to COVID-19 despite the alternative data ascertainment.

The information for subjects who dies during the study and withdrew from the study due to COVID-19 will be recorded in the eCRF and the information for subjects who had alternative data ascertainment at Month 12 or missed their Month 12 visit due to COVID-19 will be documented as protocol deviation.

In addition, a summary table of COVID-19 related protocol deviation will be provided which contains the number (%) of subjects with at least one protocol deviation and the number (%) of subjects in each category for each study arm. The table will also present the summary statistics for major protocol deviations and important protocol deviations, respectively.

For subjects who missed the protocol-defined Month 12 BCVA assessment due to COVID-19, the following measures will be implemented. As a note, these data imputations and/or handling supersede any subsequent data imputation described in this document and will only be used for subjects and visits impacted by COVID-19.

- Both alternative data ascertainment (assessment at local non-study sites as well as out of window visits) will be included as primary analysis for all BCVA related endpoints, with details specified in the following bullets:
 - Where the Month 12 BCVA assessment is performed at local non-study sites with no further ad-hoc visit, the non-study site assessment is used as the Month 12 assessment in the primary analysis.
 - Where the Month 12 BCVA assessment is performed at local non-study sites with a further ad-hoc visit within 30 days from the assessment at non-study sites, the ad-hoc assessment is used as the Month 12 assessment in the primary analysis.
 - Where the Month 12 BCVA assessment is performed at local non-study sites with a further ad-hoc visit 31 days or more from the local non-study site assessment, the local non-study site assessment is used as the Month 12 assessment in the primary analysis.
- For subjects who withdraw from the study due to COVID-19, die during the study due to COVID-19, or fail to perform the Month 12 assessment despite the implemented alternative data ascertainment measures, the Month 12 assessment is considered as missing and missing data handling specified in Section 10 will be applied.

The rationale for including alternative data ascertainment, especially out of window visits in the primary analysis is the following: 1) It is in line with FDA and EMA guidance (U. S. Food and Drug Administration 2020, EMA 2020) on handling analysis during COVID-19 pandemic; 2) No further improvement in the treated patients is expected after the initial response around roughly 1-3 months, if any, post one-time injection of this gene therapy. Therefore, including the out of window visit, especially the visits beyond Month 12 scheduled window for the treated patients is considered a conservative approach considering potential trend of natural disease progression in the long-term follow up; 3) Very slow progression is expected in untreated control patients. The natural history study NIGHT showed an average of 0.5 letters of vision loss in untreated patients during 20 months follow up. Therefore, minimum impact on the analysis is expected from the usage of visits a few months post protocol defined window for the untreated patients, especially for the primary endpoint proportions of >= 15 letters increase from the baseline in BCVA.

Sensitivity analysis will be performed on the primary endpoint and the key secondary endpoints if applicable. The main analyses described in Section 10.1 and Section 10.2 will be repeated as follows:

- On the ITT population excluding subjects who withdraw from the study or died due to COVID-19 without any imputations, but include data collected by alternative ascertainment approaches.
- On the ITT population, where assessments performed at local non-study sites are replaced by the ad-hoc visit assessment (where available), irrespective of the interval between the ad-hoc visit and the local non-study site visit.
- On the ITT population, multiple imputation based on missing at random (MAR) will be applied to impute the data collected by alternative ascertainment approaches with Month 12 visit more than 2 months prior or 3 months after the protocol defined visit window or data missing from early termination or death due to COVID-19. In this

analysis, with extra scientific rigor, multiple imputation will also be applied to Month 12 BCVA collected more than 2 months prior or 3 months after the visit window not due to COVID-19. Assuming the BCVA at different visits follows a multivariate normal distribution, the Monte Carlo Markov Chain (MCMC) will be implemented to impute all missing data and the Month 12 BCVA collected more than 2 months prior or 3 months after the visit window (Schafer 1997, Schafer 1999). Each imputed data for continuous endpoint, analysis of covariance (ANCOVA) model including surgical group, baseline value of the assessment, and study arms will be applied. For binary endpoint, the proportion difference and the corresponding standard error between the treatment groups (i.e. high dose vs. placebo, low dose vs. placebo) will be calculated for each imputed dataset using the two-sample Binomial test. Analysis will be performed for each of the 100 imputed datasets and results will be combined by Rubin's rule (Rubin 1976, Rubin 1987) for inference assuming the statistics estimated from each imputed dataset are normally distributed. The Sample SAS code is in Appendix 4.

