13.6 Efficacy Analyses

Statistical tests will be performed at the alpha level of 0.05 (unless otherwise specified). Statistical tests and 95% CIs will be 2-sided.

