14.4.2 Binary endpoint

/*** compute the proportion difference and the corresponding standard error between the treatment groups (i.e. high dose vs. placebo, low dose vs. placebo) for each imputed dataset. Use Rubin's Rule to combine the results ***/

```
PROC MIANALYZE data=propest;
modeleffects prop_diff;
stderr se_diff;
ods output parameterestimates = PARMS;
run;
```

14.5 Appendix 5: Linear Mixed Model for Study Eye vs Fellow Eye Comparison – Sample SAS Code

PROC MIXED DATA=dset; /* assumes data presented in rows */ CLASS trt eye subject; /* be careful of the sequences of the variable here */ /* see notes later */ MODEL var_chg= eye trt eye*trt var bl/ DDFM=KENWARDROGER; REPEATED eye / SUBJECT=subject TYPE=UN R RCORR RI; LSMEANS eye*trt; ESTIMATE 'high dose: study eye vs fellow eye' eye 1 -1 eye*trt 1 -1 0 0 0 0; ESTIMATE 'low dose: study eye vs fellow eye' eye 1 -1 eye*trt 0 0 1 -1 0 0; ESTIMATE 'control: study eye vs fellow eye' eye 1 -1 eye*trt 0 0 0 0 1 -1; /* the variable 'eye' indicates whether the data are study eye or fellow eye */ /* 1 is associated to the study eye data */ /* -1 is associated to the fellow eye data */ /* treatment is coded as 1-high dose, 2-low dose, 0-control */ /* note the sequence of variables in the CLASS statement is very tricky */ $/\star$ in order for the ESTIMATE statement to work correctly: /* if it appears in CLASS statement as 'eye trt subject', then the ESTIMATE */ */ /* statement has to be, for example, /* ESTIMATE 'high dose:study eye vs fellow eye' eye 1 -1 eye*trt 1 0 0 -1 0 0; */ /* When interaction term is added, this statement must be modified

RUN;

*/

*/

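### The multiple-imputation sensitivity analysis of the binary endpoints swaps Fisher's exact test for a normal-theory test with an undefined standard error; for high dose v control it is easier to pass than the primary test

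*SAP*

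**What the plan says.** The primary endpoint (SAP 10.1) is tested by unstratified Fisher's exact test in the ITT population, with a missing Month 12 value counted as failure. Boschloo's test with a Berger-Boos correction is supportive, because the SAP regards Fisher's test as too conservative when events are few. The confidence interval for the difference is Miettinen-Nurminen.

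SAP 5.5 introduces three COVID-19 sensitivity analyses as repeats of the main analyses in 10.1 and 10.2. In the third, missing Month 12 values, and those far outside the visit window, are multiply imputed 100 times. For binary endpoints the difference in proportions and its standard error "will be calculated for each imputed dataset using the two-sample Binomial test", and the results are combined by Rubin's rule on the assumption that they are normally distributed. The code comment in Appendix 4 (14.4.2) says to "compute the proportion difference and the corresponding standard error between the treatment groups" and passes `prop_diff` and `se_diff` to PROC MIANALYZE. No formula for `se_diff` appears in either place.

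SAP 3.6 assumes that a 15-"letter BCVA gain would not be observed in subjects without CHM treatment", and sizes the trial conservatively for a single such control responder.

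**The concern.** A standard error for a difference in proportions, referred to a normal or t distribution, works poorly when one arm has 0 or 1 events. With no control responders the unpooled formula gives the control arm zero variance. The plan uses exact or score methods for the same data elsewhere, so this step departs from its own approach.

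The purpose of the analysis is to ask whether the primary conclusion survives a different treatment of missing data. If the test changes at the same time, a significant result may come from the easier test and not from the imputed values. A result such as 4 v 0 or 5 v 0 would fail the primary test, and this analysis could then be cited in its support. If the primary test passes, agreement adds little, because the check is the easier hurdle.

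**Working it through.** **Inputs.** Two-sided 0.05 (Protocol 13.6: "Statistical tests will be performed at the alpha level of 0.05 (unless otherwise specified"; "Statistical tests and 95% CIs will be 2-sided"). Arm sizes from SAP 3.6: "Approximately 160 subjects will be enrolled in the study (64, high dose group; 32, low dose group; 64, control group". Rates from SAP 3.6: "Assuming that 16.7% of the treated subjects will gain" at least 15 letters, with 0 control responders, or 1 of 64 in the conservative case. The 10% rate used below is my assumption, for a treatment effect weaker than planned.

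**The plan's own figures.** Exact enumeration of the two-sided Fisher test gives 92.3% power for 56 per arm at 16.7% v 0% (stated: at least 90%). With 64 per arm and exactly 1 control responder it gives 85.9%, consistent with the sample size being "needed to ensure 85% power in case 1 patient in the untreated control group" responds. Both are reproduced.

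**Formulas.** With a of n1 active and b of n2 control responders, p1=a/n1, p2=b/n2 and p̄=(a+b)/(n1+n2):
- unpooled SE = √[p1(1−p1)/n1 + p2(1−p2)/n2]
- pooled SE = √[p̄(1−p̄)(1/n1+1/n2)]
- z = (p1−p2)/SE

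**4 v 0 at 64 v 64.** The difference is 0.0625.
- Unpooled: √(0.0625×0.9375/64 + 0) = 0.03026, z=2.07, p=0.039.
- Pooled: p̄=4/128=0.03125, √(0.03125×0.96875×2/64) = 0.03076, z=2.03, p=0.042.
- Fisher: 2×(64·63·62·61)/(128·127·126·125) = 2×0.0596 = 0.119.

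**Other tables, 64 v 64, nothing imputed:**

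| Responders | Unpooled | Pooled | Fisher | Boschloo as planned (doubled one-sided) |
|---|---|---|---|---|
| 4 v 0 | 0.039 | 0.042 | 0.119 | 0.071 |
| 5 v 0 | 0.020 | 0.023 | 0.058 | 0.032 |
| 6 v 1 | 0.049 | 0.052 | 0.115 | 0.070 |
| 7 v 1 | 0.026 | 0.029 | 0.062 | 0.038 |

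The fewest active responders needed for p<0.05 with 0, 1 and 2 control responders are 4, 6, 8 (unpooled), 4, 7, 8 (pooled) and 6, 8, 10 (Fisher).

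**How often the two tests disagree.** At true rates of 10% v 0% there are no control responders, so the discordant tables are 4 v 0 and 5 v 0. Their binomial probabilities with n=64 are 0.114 and 0.152, which sum to 0.266. So 27% of trials are significant here but not by Fisher, with either standard error. At 16.7% v 1/64, full enumeration gives 10% unpooled and 9% pooled. The reverse (Fisher significant, this test not) did not occur in either scenario.

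**With imputation.** I simulated Rubin-pooled results against Fisher with missing as failure, assuming SD 6 letters, between-visit correlation 0.7 and values missing completely at random. At 10% v 0.5%, the imputation analysis alone was significant in about 27%, 29% and 31% of trials with 0%, 5% and 10% of Month 12 values imputed (unpooled). Some of that rise comes from the missing-as-failure rule and not from the test.

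**The case against.** **Fisher is not a neutral benchmark.** The SAP itself calls it conservative for few events, and its Boschloo test also passes 5 v 0 and 7 v 1. This stands, and it accounts for part of the gap. It does not account for 4 v 0, which passes here with either standard error, or for 6 v 1, which passes with the unpooled one; Boschloo rejects neither.

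**The analysis gates nothing.** The hierarchy in SAP 10.3 depends on the primary test. The other two COVID-19 analyses rerun the main analysis, and 10.4.1 adds last observation carried forward for binary endpoints. This stands and limits the severity.

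**A reader might infer that the SAP specifies a Wald test whose error exceeds 5%.** The documents do not support this. The standard error is undefined. At a common 5% rate, error is 6.2% unpooled but 4.7% pooled (Fisher 1.2%). At 1/64, the regime the design assumes, it is about 1.3% with either. The unpooled error first passes 5% at a common rate of about 3.5%. In a simulation at a 5% rate (assumed SD 9, correlation 0.7, values missing completely at random) it fell to 4.1% with 5% imputed and 2.7% with 15%.

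**A reader might also infer that the low-dose comparison is liberal.** The unpooled error at 32 v 64 and a 5% rate is 8.5%, but only 0.7% favours low dose. In that direction the unpooled test is stricter than Fisher: 3 v 0 gives 0.069 against 0.035. With a pooled SE the direction can reverse: for 2 v 0, p̄=2/96, SE=0.0309, z=2.02, p=0.043, against Fisher (32·31)/(96·95)=0.109. That is a further reason to define `se_diff`, not evidence that the plan is liberal there.

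**Conclusion.** The point holds for high dose v control. The planned method is poorly suited to the 0 or 1 control responders that the design expects, and it is easier to pass than the primary test. At 4 v 0 and 5 v 0 this does not depend on which standard error is meant. The 27% discordance rests on an assumed true rate of 10% v 0%; at the design's own 16.7% v 1/64 it is 9% to 10%. Both are for complete data at the planned arm sizes.

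The consequence is one of interpretation: test and missing-data handling change together, so neither agreement nor disagreement with the primary result can be attributed to the missing data. No claim of inflated type I error, or of leniency in the low-dose comparison, is made. Because the analysis is supportive, this is a correction that should be made and not a threat to the primary inference.

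**What to change.** 1. Define `se_diff` in SAP 5.5 and Appendix 4.
2. In each imputed dataset, compute the difference and its standard error with a sparse-data method before applying Rubin's rule. One option is Agresti-Caffo, which adds one success and one failure per arm. The other is a score-based standard error consistent with the planned Miettinen-Nurminen interval.
3. Report the same statistic on the data with missing counted as failure, beside the imputed result. The comparison then isolates the missing-data handling.

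Worked example, Agresti-Caffo at 4 v 0: 5/66 − 1/66 = 0.0606; SE = √(0.0758×0.9242/66 + 0.0152×0.9848/66) = 0.0359; z=1.69; p=0.091. Likewise 6 v 1 becomes 0.081, 5 v 0 becomes 0.049 and 7 v 1 becomes 0.045.

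The cost is one programming step and less favourable p-values. The change narrows the gap to Fisher without closing it: 5 v 0 and 7 v 1 stay below 0.05, in line with the planned Boschloo test but not with Fisher. Step 3 is therefore needed as well.
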